9.3 Populations for Analyses

The following populations are defined:

Population	Description
Enrolled	All participants who sign the informed consent form are allocated to treatment
Full Analysis Set (FAS)	All participants who are enrolled and receive at least 1 dose of study treatment.
Response Analysis Set (RAS)	The response analysis set will consist of all participants who are enrolled and receive at least 1 dose of IP and have at least 1 post baseline primary efficacy measurement.
Safety Analysis Set (SAF)	All participants who take at least one dose of IP.
Pharmacokinetic analysis set (PKAS)	The PKAS consists of the administered population for which pharmacokinetics data are available for at least 1 time point. Additional participants may be excluded from the PKAS at the discretion of the pharmacokineticist.
Pharmacodynamic analysis set (PDAS)	The PDAS will include the participants from the administered population for whom sufficient pharmacodynamic measurements were collected. The PDAS will be used for all analyses of pharmacodynamic data.
DLT Evaluation Analysis Set (DEAS)	The DEAS is defined as all participants in the SAF by excluding participants who meet any of the following criteria: Participant is discovered to have enrolled without fully satisfying eligibility criteria. Participant received less than the planned dose in cycle 1 for reasons other than DLT. Participant has no DLT and withdraws from the study before the end of the DLT evaluation period. The DEAS will be used for the analysis of DLT data.

DLT: dose limiting toxicity

9.4 Statistical Analyses

A statistical analysis plan (SAP) will be written to provide details of the analysis, along with specifications for tables, listings and figures to be produced. Changes from the planned analyses in the final SAP that impact the statistical analyses will be justified in the clinical study report (CSR).

9.4.1 General Considerations

In general, data will be summarized with descriptive statistics for continuous endpoints, and frequency and percentage for categorical endpoints, unless otherwise specified. Percentages by categories will be based on the number of participants with no missing data (i.e., will add up to 100%).

Baseline will be defined as the last nonmissing observation prior to the first administration of IP, unless otherwise specified.

In general, dose escalation and safety lead-in data will be summarized by dose level. Phase 2 data will be summarized by monotherapy and combination therapy arms and by tumor types, unless specified otherwise.

Demographics and baseline characteristics will be summarized for all treated participants.

The number and percentage of participants who completed and discontinued treatment and reasons for treatment discontinuation will be presented for all enrolled participants, for participants in the safety analysis set (SAF). Similar tables for screening disposition, follow-up period disposition and survival follow-up disposition will also be presented for all treated participants. All disposition details and dates of first and last evaluations for each participant will be listed.

Previous and concomitant treatment and medical history will be listed. IP exposure will be summarized using descriptive statistics and will be listed.

9.4.2 Analysis of Efficacy

Binary efficacy endpoint analysis will be conducted on the response analysis set (RAS), while time to event endpoints will be conducted on the full analysis set (FAS). The interpretation of results of the primary efficacy endpoint will be based on the RAS. Tumor related analyses are summarized based on RECIST v1.1 and iRECIST.

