9.4.2.2 Sensitivity Analysis

The same analysis used for the primary endpoint as described in [Section 9.4.2.1.1 Primary Analysis] will be conducted for the following:

- iORR with unconfirmed response by independent central review
- iORR with confirmed response by investigator assessment
- iORR with unconfirmed response by investigator assessment

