## **4 ANALYSIS SETS**

In accordance with International Conference on Harmonization (ICH) recommendations in guidelines E3 and E9, the following analysis sets will be used for the analyses. Full Analysis Set (FAS) and Response Analysis Set (RAS) will be used for efficacy analysis. Safety Analysis Set (SAF) will be used for the analyses of safety variables. Pharmacokinetic Analysis Set (PKAS) will be used for pharmacokinetic analyses. Pharmacodynamics analysis

set (PDAS) will be used for all analyses of pharmacodynamics data. The data from all participants who were enrolled in the study will be included in the data listings. All enrolled participants are those who signed the informed consent form and were assigned a participant number.

For each dose level, the number and percentage of participants will be characterized for all treated participants and by each analysis set.

Population	Description
Enrolled	All participants who sign the informed consent form and are allocated to treatment.
Full Analysis Set (FAS)	All participants who are enrolled and receive at least one dose of study treatment.
Response Analysis Set (RAS)	The response analysis set will consist of all participants who are enrolled and receive at least one dose of IP and have at least one post baseline primary efficacy measurement.
Safety Analysis Set (SAF)	All participants who take at least 1 dose of IP.
Pharmacokinetic Analysis Set (PKAS)	The PKAS consists of the administered population for which pharmacokinetics data are available for at least one time point. Additional participants may be excluded from the PKAS at the discretion of the pharmacokineticist.
Pharmacodynamic Analysis Set (PDAS)	The PDAS will include the participants from the administered population for whom sufficient pharmacodynamic measurements were collected. The PDAS will be used for all analyses of pharmacodynamic data.
DLT Evaluation Analysis Set (DEAS)	
The DEAS is defined as all participants in SAF excluding participants who meet any of the following criteria:
 

• Participant is discovered to have enrolled without fully satisfying eligibility criteria.

• Participant received less than the planned dose in cycle 1 for reasons other than DLT.

• Participant has no DLT and withdraws from the study before the end of DLT evaluation period.

 
The DEAS will be used for the analysis of DLT data.

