**Table 2 iPFS Definition**

iPFS		
Situation	Date of Event or Censor	Outcome
No evaluable post-baseline imaging assessments, no death	Date of first dose (Day 1)	Censor
Participant did not receive new anti-cancer therapy (ACT):		
iCPD	First date where iUPD criteria are met	Event
No iCPD, but death recorded on eCRF	Date of death	Event
No iCPD nor death and not in one of the following cases : a) if the participant stops protocol treatment because they were not judged to be clinically stable, b) no further response assessments are done (because of participant refusal, protocol non-compliance, or participant death); c) the next timepoint responses are all iUPD, and iCPD never occurs;	Date of last radiological assessment	Censor
No iCPD nor death and is in one of the following cases : a) if the participant stops protocol treatment because they were not judged to be clinically stable, b) no further response assessments are done (because of participant refusal, protocol non-compliance, or participant death); c) the next timepoint responses are all iUPD, and iCPD never occurs;	First date where iUPD criteria are met	Event
Participant received new anti-cancer therapy (ACT):		
No progression before new ACT	Date of last radiological assessment before start of new anti-cancer therapy	Censor
iCPD before new ACT	First date where iUPD criteria are met	Event
iUPD before new ACT and not in one of the following cases: a) if the participant stops protocol treatment because they were not judged to be clinically stable, b) no further response assessments are done (because of participant refusal, protocol non-compliance, or participant death); c) the next timepoint responses are all iUPD, and iCPD never occurs;	Date of last radiological assessment before start of new anti-cancer therapy	Censor
Table continued on next page		

iPFS		
Situation	Date of Event or Censor	Outcome
iUPD before new ACT and is in one of the following cases : a)if the participant stops protocol treatment because they were not judged to be clinically stable, b) no further response assessments are done (because of participant refusal, protocol non-compliance, or participant death); c) the next timepoint responses are all iUPD, and iCPD never occurs;	First date where iUPD criteria are met	Event
Missed <math>\geq 2</math> scheduled radiological assessments		

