**Table 3 PFS Definition**

PFS		
Situation	Date of Event or Censor	Outcome
No evaluable post-baseline imaging assessments, no death	Date of first dose (Day 1)	Censor
Participant did not receive new anti-cancer therapy (ACT):		
Radiographical progression documented per RECIST v1.1	Date of radiological disease progression	Event
No radiographical progression, but death recorded on eCRF	Date of death	Event
Neither radiographical progression nor death	Date of last disease assessment	Censor
Participant received new anti-cancer therapy (ACT):		
Radiographical progression documented per RECIST v1.1 after new ACT	Date of last radiological assessment before start of new anti-cancer therapy	Censor
Radiographical progression documented per RECIST v1.1 before new ACT	Date of radiological disease progression	Event
No radiographical progression before new ACT but death recorded	Date of last radiological assessment before start of new anti-cancer therapy	Censor
No radiographical disease progression nor death	Date of last radiological assessment before start of new anti-cancer therapy	Censor
Missed >=2 scheduled radiological assessments		
If radiographical progression or death occurs after missing 2 scheduled radiological assessments	Date of last radiological assessment before missing 2 scans	Censor

PFS = Date of Event or Censor – Date of First Dose +1

Missing 2 scheduled imaging assessments:

Missing 2 scheduled imaging assessments is defined as the gap between two imaging assessments as more than 140 days (2.5 times the scheduled imaging assessment interval (2.5 x 56 days)). Imaging assessments after first iUPD will be excluded in PFS derivation.

Note: Participant cannot be censored at “NE”. If NE is the only previous assessment, then PFS will be censored at Day 1.

To apply the cut-off date to PFS is to exclude those tumor assessments after cut-off date and anti-cancer therapy date after cut-off date in the analysis.

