## **6 STATISTICAL METHODOLOGY**

### **6.1 General Considerations**

For continuous variables, descriptive statistics will include the number of participants (n), mean, standard deviation, median, minimum, and maximum. When needed, the use of other percentiles (e.g., 10%, 25%, 75% and 90%) will be reported in the relevant section. In addition, for plasma concentrations and continuous PK parameters, the coefficient of variation (CV) and the geometric mean will also be calculated. Frequencies and percentages will be displayed for categorical data. Percentages by categories will be based on the number of participants with no missing data, i.e., will add up to 100%.

Summaries based on FAS and RAS (e.g., disposition, baseline, and efficacy data) will be presented by planned treatment, unless specifically stated otherwise. Safety analysis and other summaries based on SAF, PKAS or PDAS will be presented by actual dose level received.

Baseline is defined as the last available measurement prior to the first dose of IP.

Unless otherwise specified, all summaries will be presented overall, by dose level, and by phase.

All data processing, summarization, and analyses will be performed using Statistical Analysis Software (SAS)® Version 9.4 or higher on Linux. Specifications for table, figure, and listing (TLF) formats can be found in the TLF specifications for this study.

Study day will be calculated in reference to the first dose date. For assessments conducted before the first dose, study day will be calculated as (assessment date – first dose date). For assessments conducted on or after the first dose, study day will be calculated as (assessment date – first dose date + 1).

For the definition of subgroups of interest, please refer to Section [6.8](#).

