## **6.4 Analysis of Efficacy**

Efficacy analysis will be conducted on the FAS and RAS (RAS for response-related analyses, FAS for survival and other time-to-event analyses). Best overall responses are summarized based on iRECIST and RECIST 1.1. Efficacy analyses will be summarized by dose level, phase, and overall. Swimmer plots will be produced displaying participants' overall disease response experience, spider plots to display percent change in tumor size, and waterfall plots to display maximum tumor shrinkage rate.

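### Response and disease control rates are planned only on the Response Analysis Set, with no all-treated rate, so any treated participant who is never assessed leaves the denominator

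*Protocol*

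**What the plan says.** Protocol 9.4.2 assigns binary efficacy endpoints to the RAS and time-to-event endpoints to the FAS, and adds: "The interpretation of results of the primary efficacy endpoint will be based on the RAS". Under protocol 9.3 the FAS is everyone enrolled who received at least one dose. To be in the RAS a participant must also "have at least 1 post baseline primary efficacy measurement". SAP section 4 repeats the condition ("have at least one post baseline primary efficacy measurement"), and SAP 6.4 keeps the split: "RAS for response-related analyses, FAS for survival and other time-to-event analyses".

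The sensitivity analyses in protocol 9.4.2.2 change the reader or the confirmation requirement, for example "iORR with confirmed response by investigator assessment". SAP 6.4.1.1 and 6.4.2.1 to 6.4.2.3 give iORR, ORR, iDCR and DCR by investigator assessment, with and without confirmation. None of these analyses changes the analysis set. Neither document plans a response or disease control rate on all treated participants, and neither has a rule that counts an unassessed treated participant as a failure.

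**The concern.** RAS membership depends on something that happens after treatment starts. A participant who dies, deteriorates or withdraws before the first scan may have no post-baseline measurement and so leaves the denominator, sometimes because treatment failed. Such a participant cannot have contributed to the numerator, since iCR, iPR, iSD, CR, PR and SD all require a post-baseline assessment. Each exclusion therefore removes a certain failure and nothing else, so the reported rate can equal or exceed the all-treated rate but never fall below it.

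What is at stake is how the remaining efficacy results read. SAP section 1 says the study ended early, with no combination treatment and no central review data. What is left is investigator-assessed rates by dose level, phase and overall. In groups that small, one exclusion moves the estimate visibly.

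**Working it through.** **Inputs.** The set definitions are in protocol 9.3 and SAP section 4. The Clopper-Pearson 95% interval is specified in protocol 9.4.2.1.1 and SAP 6.4.1.1. Protocol 2.3.1.1 reports 4 participants dosed at the first level by 06 May 2022. Protocol 9.2 plans about 12 participants in dose escalation, and protocol 4.1 sets a maximum of 43 per single-agent cohort. The documents give no unassessed share, so every value of m below is an assumption. They also give no all-treated rate to reproduce.

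**Formula.** Let N be the number treated, m the number unassessed and r the number of responders (or participants with disease control).

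- RAS rate = r/(N − m)
- All-treated rate = r/N
- Ratio = N/(N − m) = 1/(1 − q), with q = m/N

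At q = 5% the ratio is 1/0.95 = 1.05. At q = 10% it is 1/0.90 = 1.11.

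**Results**, with Clopper-Pearson 95% intervals in brackets:

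| Assumed case | RAS | All treated (FAS) |
|---|---|---|
| 4 treated, 1 unassessed, 1 responder | 1/3 = 33.3% (0.8 to 90.6) | 1/4 = 25.0% (0.6 to 80.6) |
| 4 treated, 1 unassessed, 0 responders | 0/3, upper limit 70.8% | 0/4, upper limit 60.2% |
| 6 treated, 1 unassessed, 1 responder | 1/5 = 20.0% (0.5 to 71.6) | 1/6 = 16.7% (0.4 to 64.1) |
| 6 treated, 1 unassessed, 3 with disease control | 3/5 = 60.0% (14.7 to 94.7) | 3/6 = 50.0% (11.8 to 88.2) |
| 12 treated, 1 unassessed, 1 responder | 1/11 = 9.1% (0.2 to 41.3) | 1/12 = 8.3% (0.2 to 38.5) |
| 43 treated, 4 unassessed, 8 responders | 8/39 = 20.5% (9.3 to 36.5) | 8/43 = 18.6% (8.4 to 33.4) |

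The last row shows the effect at planned cohort size. With no responders the point estimate is 0% on either set. Only the upper limit changes: for 0/3 it is 1 − 0.025^(1/3) = 70.8%, and for 0/4 it is 1 − 0.025^(1/4) = 60.2%.

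**The case against.** **The RAS may be the intended target.** It is prespecified, and the hypotheses in protocol 9.1 name no denominator. Protocol 4.1 lets the sponsor replace phase 2 participants who fall outside the RAS. All this is consistent with a response-evaluable estimand, common in early-phase oncology. That is a fair reason to keep the RAS result. It does not explain why the all-treated rate is absent altogether. The claim here is only that the RAS rate is at or above the all-treated rate.

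**Few participants should be missed.** Inclusion criterion 9 requires a life expectancy of at least 12 weeks. Protocol 7.1 schedules imaging every 8 weeks regardless of treatment delays, and protocol 8.2 keeps participants who stop treatment in follow-up. This stands, and it is why the effect is probably modest.

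**A reader can rebuild the rate.** SAP section 4 and 6.2.1 report the size of each analysis set, and SAP 6.4 summarises best overall response on the same breakdown, so r and N can be recovered. That is true, but it leaves the all-treated rate and interval to the reader instead of making them planned output.

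**Two inferences go too far.** A reader might take the row "No evaluable post-baseline imaging assessments, no death" in SAP Tables 2 and 3 as proof that the SAP keeps these participants for iPFS and PFS while dropping them all from response. The row concerns evaluable imaging, whereas the RAS asks only for a measurement. The table notes treat a not-evaluable (NE) reading as an assessment, so a participant with only NE scans may be in the RAS and count as a non-responder. Nor is the row "No radiographical progression, but death recorded on eCRF" limited to participants without scans.

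A reader might also infer from SAP 6.1 ("Percentages by categories will be based on the number of participants with no missing data") that unassessed participants would be dropped even on the FAS. That sentence concerns percentages by category, and the response endpoints have their own definitions, so this is conjecture.

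**Conclusion.** The point holds as a gap in the planned reporting. All four response and disease control rates rest on a set that can lose certain failures after treatment starts, and no planned analysis shows the rate without that loss. The direction follows from arithmetic. The size depends on an unassessed share that the documents do not give: a factor of 1.05 at an assumed 5% and 1.11 at 10%, but 4/3 when 1 of 4 treated participants is unassessed. The intervals in such small groups are wide on either denominator, and SAP 6.4 schedules estimates, not an efficacy decision. The matter is therefore one of accurate reporting and would not overturn a conclusion.

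A reader might go further and infer that the one-sided 0.05 error rate in protocol 9.2 fails, because the boundary tables in protocol 4.1 count treated participants while those outside the RAS may be replaced. The documents do not support this. With one counting unit throughout, the stated two-stage rules give exact type I error of 0.048 (single agent), 0.042 (SS and MRCL combination) and 0.047 (ovarian combination). Exceeding 0.05 needs a null rate defined on treated participants together with boundaries that count evaluable ones, and no section says that.

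**What to change.** In SAP 6.4, and in protocol 9.4.2 for consistency, make the FAS the main set for iORR, ORR, iDCR and DCR, each with its Clopper-Pearson interval. State that a treated participant with no post-baseline assessment counts as a non-responder and as not disease-controlled. Keep the RAS results as supportive.

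The FAS is already defined in both documents, so the change needs only wording and the corresponding table rows, with no new data. The downside is that reported rates will be slightly lower wherever someone is unassessed and at least one participant succeeds.

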9.4.2.1 Analysis of Primary Endpoint

9.4.2.1.1 Primary Analysis

iORR is defined as the proportion of participants for each dose level whose best overall response is rated as confirmed iCR or iPR per iRECIST by independent central review. iORR for each dose level will be calculated and its 95% confidence interval will be constructed by Clopper-Pearson method.

9.4.2.2 Sensitivity Analysis

The same analysis used for the primary endpoint as described in [Section 9.4.2.1.1 Primary Analysis] will be conducted for the following:

- iORR with unconfirmed response by independent central review
- iORR with confirmed response by investigator assessment
- iORR with unconfirmed response by investigator assessment

9.4.2.3 Analysis of Secondary Endpoints

Objective Response Rate per RECIST v1.1 (ORR):

ORR is defined as the proportion of participants for each dose level whose best overall response is rated as CR or PR per RECIST v1.1. The same analysis used for the primary endpoint as described in [Section 9.4.2.1.1 Primary Analysis] will be conducted for the following:

- ORR with confirmed response by independent central review
- ORR with unconfirmed response by independent central review
- ORR with confirmed response by investigator assessment
- ORR with unconfirmed response by investigator assessment

Disease Control Rate per iRECIST (iDCR):

iDCR is defined as the proportion of participants for each dose level whose best overall response is rated as confirmed iCR, iPR or stable disease (iSD) per iRECIST. iDCR for dose level will be calculated and its 95% confidence interval will be constructed by Clopper-Pearson method by independent central review and investigator assessment.

Disease Control Rate per RECIST v1.1 (DCR):

DCR is defined as the proportion of participants for each dose level whose best overall response is rated as confirmed CR, PR or SD per RECIST v1.1. DCR by dose level will be calculated and its 95% confidence interval will be constructed by Clopper-Pearson method by independent central review and investigator assessment.

Overall Survival (OS):

OS is defined as the time from the date of first dose until the date of death from any cause (death date - first dose date + 1). For a participant who is not known to have died by the end of study follow-up, OS is censored at the date of last contact (date of last contact - first dose date + 1). The distribution of OS will be estimated for each dose level using Kaplan-Meier methodology.

Progression-free Survival per iRECIST (iPFS):

iPFS is defined as the time from the start of the study treatment until death from any cause or radiographic disease progression assessed per iRECIST by independent central review and investigator assessment, whichever occurs first. The distribution of iPFS will be estimated for each dose level using Kaplan-Meier methodology.

Progression-free Survival per RECIST v1.1 (PFS):

PFS is defined as the time from the start of the study treatment until death from any cause or radiographic disease progression assessed per RECIST v1.1 by independent central review and investigator assessment, whichever occurs first. The distribution of PFS will be estimated for each dose level using Kaplan-Meier methodology.

Duration of Response per iRECIST (iDOR):

iDOR will be calculated only for the subgroup of participants with confirmed response iCR/iPR per iRECIST by independent central review and investigator assessment. The distribution of iDOR will be estimated for each dose level using Kaplan-Meier methodology.

Duration of Response per RECIST v1.1 (DOR)

DOR will be calculated only for the subgroup of participants with confirmed response CR/PR per RECIST v1.1 by independent central review and investigator assessment. The distribution of DOR will be estimated for each dose level using Kaplan-Meier methodology.

